11.2 Reporting to FDA

- Serious adverse events will be forwarded to FDA by the IND Sponsor (Safety Project Manager IND Office) according to 21 CFR 312.32.

It is the responsibility of the PI and the research team to ensure serious adverse events are reported according to the Code of Federal Regulations, Good Clinical Practices, the protocol guidelines, the sponsor's guidelines, and Institutional Review Board policy.

11.3 Investigator Communication with Supporting Companies

- Adverse events classified as "serious" require expeditious handling and reporting to BMS to comply with regulatory requirements.
- All SAEs whether related or unrelated to nivolumab or ipilimumab must be immediately reported to BMS (by the investigator or designee) within 24 hours of becoming aware of the event, using the M. D. Anderson SAE forms. If only limited information is initially available, follow-up reports are required. The original SAE form must be kept on file at the study site.

All SAEs should be faxed (or emailed) to BMS at:

Global Pharmacovigilance & Epidemiology

Bristol-Myers Squibb Company

[contact]

Email: [contact]

- For studies conducted under an Investigator IND, any event that is both serious and unexpected must be reported to the FDA as soon as possible and, in no event, later than 7 days (death or life-threatening event) or 15 days (all other SAEs) after the investigator's or institution's initial receipt of the information. The investigator will provide BMS with a simultaneous copy of all adverse events filed with the FDA. SAEs will be reported on the MDACC SAE Form.

- AE Reporting Period: For nivolumab and ipilimumab, all AEs must be collected which occur after the first dose through within 100 days of discontinuation of dosing or completion of the patient's participation in the study if the last scheduled visit occurs at a later time. In addition, the Investigator should notify BMS of any SAE that may occur after this time period which they believe to be certainly, probably, or possibly related to nivolumab and/or ipilimumab.
 - [contact]

Notes:

- Cancer/Overdose: An overdose is defined as the accidental or intentional ingestion of any dose of a product that is considered both excessive and medically important. For reporting purposes, any form of overdose, regardless of adverse outcome, will be considered as an important medical event and reported immediately to BMS.
- Hospitalizations (exceptions): Criteria for hospitalizations not reported as SAEs include admissions for:
 - Planned as per protocol medical/surgical procedure
 - Routine health assessment requiring admission for baseline/trending of health status documentation (e.g., routine colonoscopy)
 - Medical/surgical admission for purpose other than remedying ill health state (planned prior to entry into study trial; appropriate documentation required)
 - Admission encountered for other life circumstance that carries no bearing on health status and requires no medical/surgical intervention (e.g. lack of housing, economic inadequacy, care-giver respite, family circumstances, administrative)

11.4 Pregnancy

Patients must agree to use adequate contraception (barrier method of birth control) prior to study entry, and for up to 23 weeks after the last study drug dose (for female study participants) or up to 31 weeks after the last study drug dose (for male study participants). The treating physician, principle investigator and BMS should be notified immediately, should a patient or patient's sexual partner become pregnant or suspect she is pregnant while participating in this study.

12.0 STATISTICAL METHODOLOGY

12.1 Preliminaries and Objectives

This is a randomized, pilot trial of nivolumab (Arm A) or nivolumab + ipilimumab (Arm B) as pre-operative treatment for patients with hepatocellular carcinoma who are eligible for surgical resection. Each patient in both Arms A and B will be given nivolumab at 240 mg every 2 weeks

for a total of 6 weeks. Patients in Arm B will additionally be treated concurrently with ipilimumab at 1mg/kg every 6 weeks. No dose increases or reductions will be allowed for nivolumab or ipilimumab. Surgical resection or post-treatment biopsy will occur within 4 weeks after finishing the last cycle of therapy. The rationale is that nivolumab and ipilimumab activate the immune system via distinct mechanisms and therefore, the combination of nivolumab and ipilimumab may result in synergistic activation of the immune system against hepatocellular carcinoma. The primary objective is to assess the safety and tolerability of nivolumab +/- ipilimumab. Secondary objectives include estimating the ORR and TTP of the 2 different arms. Exploratory objectives include evaluating the pre- and post-treatment immunological changes in tumor tissues and peripheral blood.

As of January 8, 2020, 30 patients have been enrolled and 27 patients have been randomized. The PI decided to stop enrollment since the study has reached its primary endpoint of safety.

12.2 Endpoints

12.2.1 Primary Endpoint: Safety

Safety will be recorded through the incidence of adverse events, serious adverse events and specific laboratory abnormalities (worst grade) in each treatment arm. Toxicities will be graded using the NCI CTCAE version 4.0. For trial monitoring and decisions about future trials, extreme toxicities (TOX) will be defined as any grade 3 or higher adverse event that is possibly, probably, or definitely related to any therapy received on this protocol and occur within the first 6 weeks of therapy with one exception. Any grade 3 or higher adverse event that is potentially treatable with steroids will only count as an extreme toxicity if it does not improve to grade 1 or better within 2 weeks. Additionally, a delay of greater than 3 months from the expected surgery date will count as a TOX.

Success will be predefined as having at least 13 of 15 subjects receiving their assigned therapy without grade 3 or higher adverse events necessitating a delay in the pre-established surgical resection date (a clinically driven end-point defined by the multidisciplinary MD Anderson hepatocellular cancer team).

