3.3.2 Nivolumab in Hepatocellular Carcinoma

El-Khoueiry AB, et al. presented results from the interim analysis of the phase 1/2 nivolumab trial (CA209-040) in patients with advanced hepatocellular carcinoma at the 2015 annual ASCO meeting [34]. In the presentation, the dose escalation study demonstrated safety and tolerability of nivolumab at 0.1 mg/kg to 10 mg/kg in patients with HCC due to HCV, HBV or who were uninfected with viral hepatitis. The only grade 4 adverse event was elevated lipase (1 patient) while grade 3 elevations in liver enzymes were seen in 9 patients (AST = 5, ALT = 9). 3 mg/kg was selected for the dose expansion in the uninfected and HCV cohorts; the dose escalation for the HBV cohort was ongoing. In 42 patients evaluable to response, the ORR by RECIST 1.1 criteria was 19% (8) with 2 patients achieving a complete response. The preliminary overall survival at 12 months was 62% (95% CI 42-76%). Moreover, Sangro B, et al. recently presented interim results of 214 patients in the expansion CheckMate-040 study who received Nivolumab 3 mg/kg every 2 weeks [35]. This report demonstrated a preliminary ORR = 16%.

Because of these results, a phase III study comparing nivolumab to sorafenib for patients with advanced HCC has been launched in the frontline setting with an estimated enrollment of 726 patients and primary completion date of July 2017 (NCT02576509).

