3.3.3 Summary of Results from Nivolumab Program

For a complete review of clinical information, please refer to the nivolumab Investigator Brochure.

3.3.3.1 *Summary of Safety*

In clinical trial CA209001 (n = 39), patients received a single dose of nivolumab with possible retreatment at 3 months. The most frequent adverse events (AEs) were fatigue (56%), nausea (44%), proteinuria (38%), constipation (33%), back pain (33%), dry mouth (28%), vomiting (28%), rash (26%) and dyspnea (26%). There was no clear correlation between the incidence or severity of AEs and the nivolumab dose levels (0.3, 1, 3, or 10 mg/kg IV single dose, with possible retreatment at 3 months). Among 39 (100%) patients who had at least one AE, 32 (82%) had Grade 3 or 4 AEs. Three treatment-related severe adverse events (SAEs) were reported: hypothyroidism (Grade 2), colitis (Grade 3), and anemia (Grade 2). Among 12 deaths, none were considered drug-related.

In CA209003 (n = 306), as of the database lock date of 18-March-2013, nivolumab-related AEs of any grade occurred in 75.2% of patients [36]. The most frequent drug-related AEs occurring in $\geq 5\%$ of patients included fatigue (28.1%), rash (14.7%), diarrhea (13.4%), pruritus (10.5%), nausea (9%), decreased appetite (9%), and fever (6%). The majority of AEs were low grade, with Grade 3/4 drug-related AEs observed in 14% of patients. The most common Grade 3/4 drug-related AEs occurring in $\geq 1\%$ of patients were fatigue (2%), pneumonitis (1%), diarrhea (1%), AST/ALT increase (0.3% each) Drug-related SAEs occurred in 17% of patients. Grade 3/4 drug-related SAEs occurring in $\geq 1\%$ of patients were: pneumonitis (1.3%), and diarrhea (1%). The spectrum, frequency, and severity of nivolumab-related AEs were generally similar across dose levels and histological subtypes. Other drug-related AEs included vitiligo, hepatitis, hypophysitis, and thyroiditis.

Hepatic or gastrointestinal events were managed with treatment interruption and administration of corticosteroids, and were generally completely reversible. Endocrine events were managed with hormone replacement therapy. Several patients in these categories successfully reinitiated treatment with nivolumab. Drug-related pneumonitis occurred in 3% of patients; Grade ≥ 3 pneumonitis developed in 3 patients (1%). No clear relationship was identified between the

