4.1 Inclusion Criteria

Signed written informed consent

1. Patients must give written informed consent prior to initiation of therapy, in keeping with the policies of the institution. Patients with a history of major psychiatric illness must be judged able to fully understand the investigational nature of the study and the risks associated with the therapy.

Target population

2. Patients with histologically confirmed HCC (Documentation of original biopsy for diagnosis is acceptable if tumor tissue is unavailable) or clinical diagnosis by AASLD criteria in cirrhotic subjects is required (presence of arterial hypervascularity with venous washout). For subjects without cirrhosis, histological confirmation is mandatory. The determination of resectability status will ultimately lie in the clinical judgment of the surgical oncologist and medical oncologist involved in the care of the patient.
3. Patient must have measurable disease defined as a lesion that can be accurately measured in at least one dimension (longest diameter to be recorded) and measures ≥ 15 mm with conventional techniques or ≥ 10 mm with more sensitive techniques such as MRI or spiral CT scan.
4. Patient can have had prior treatment for HCC including prior surgery, radiation therapy, local-regional therapy (ablation or arterial directed therapies), and systemic therapy including sorafenib or chemotherapy (but not anti-PD-1 or anti-CTLA-4 therapy)
5. ECOG performance status ≤ 1 .
6. Within 14 days of the first dose of study drug, patients must have adequate organ and marrow function as defined below:
 - Absolute neutrophil count $\geq 1,500/\mu\text{L}$
 - Platelets $\geq 100,000/\mu\text{L}$
 - Hgb > 9.0 g/dL (may be transfused or receive epoetin alfa [e.g., Epogen®] to maintain or exceed this level)
 - Total bilirubin ≤ 1.5 mg/dl
 - Serum creatinine ≤ 1.5 times the upper limit of normal or estimated CrCL >40 mL/min.
 - AST (SGOT) and/or ALT (SGPT) ≤ 5 X institutional upper limit of normal

Age and Sex

7. Men and women ≥ 18 years of age
8. Women of childbearing potential (WOCBP) must have a negative serum or urine pregnancy test (minimum sensitivity 25 IU/L or equivalent units of HCG) within 24 hours prior to the start of study drug.
9. Women must not be breastfeeding

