10.3.1.5 Adverse Event Monitoring

An adverse event is the appearance or worsening of any undesirable sign, symptom, or medical condition occurring after starting the study drug even if the event is not considered to be related to study drug. Medical conditions/diseases present before starting study drug are only considered adverse events if they worsen after starting study drug. Abnormal laboratory values or test results constitute adverse events only if they induce clinical signs or symptoms, are considered clinically significant, or require therapy.

Adverse events will be evaluated according to the NCI CTCAE Version 4.0 on a continuous basis starting from when the patient takes the first dose of nivolumab or ipilimumab to follow up visits. Events, such as abnormal laboratory values, considered by the principal investigator to be not clinically significant (related to the study or study drug) will not be documented. **The investigator (or physician designee) is responsible for verifying and**

providing source documentation for all adverse events and assigning the attribution for all adverse events for subjects enrolled. If abnormal lab values, which were not pre-existing or which worsened after the first dose of study drug, meet Common Terminology Criteria (CTC) for reporting as adverse events (AE), they will be documented in the AE source document and captured in the CORE/PDMS Database. For the lab results that do not meet the CTC for reporting as an AE, they will be considered not clinically significant (NCS). No additional documentation will be required to neither specify NCS lab results nor require physician investigator signature.

Adverse events will be treated appropriately. Such treatment may involve changes in nivolumab or ipilimumab therapy including possible interruption or discontinuation, starting or stopping concomitant treatments, changes in the frequency or nature of assessments, hospitalization, or any other medically required intervention. Refer to Sections 6.1-3 for treatments of nivolumab or ipilimumab infusion reaction and toxicities.

Once an adverse event is detected, it should be followed until its resolution, and assessment should be made at each visit of any changes in severity, the suspected relationship to nivolumab or ipilimumab, the interventions required to treat it, and the outcome. Reporting of adverse events will be done according to NCI CTCAE version 4.0. The following items will be recorded at least:

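### The extreme-toxicity rule requires recovery to grade 1 with no reference to baseline, so an eligible patient with raised AST/ALT at entry who returns fully to baseline still counts as a TOX

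*Combined protocol and SAP*

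**What the plan says.** Section 12.2.1 states that "Toxicities will be graded using the NCI CTCAE version 4.0" and then defines the measure: "For trial monitoring and decisions about future trials, extreme toxicities (TOX) will be defined as any grade 3 or higher adverse event". The event must be "possibly, probably, or definitely related to any therapy received on this protocol and occur within the first 6 weeks of therapy". There is one exception: an event that steroids might treat "will only count as an extreme toxicity if it does not improve to grade 1 or better within 2 weeks". The section does not mention the patient's grade before treatment.

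Inclusion criterion 6 in Section 4.1 requires, within 14 days of the first dose, "AST (SGOT) and/or ALT (SGPT) ≤ 5 X institutional upper limit of normal".

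Four other places bear on the point:

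- Section 10.3.1.5 (Adverse Event Monitoring) records abnormal laboratory values "which were not pre-existing or which worsened after the first dose of study drug" if they meet the CTC reporting criteria.
- Section 7.0 (Dose Modifications) also uses a 2-week period, but treats a fall from grade 4 to grade 3 or lower, or from grade 3 to grade 2 or lower, as a response to steroids.
- Section 11.1 follows serious adverse events until laboratory tests are back at baseline, among other end points.
- Section 3.3.2 reports, from the cited nivolumab trial in advanced HCC, that "grade 3 elevations in liver enzymes were seen in 9 patients (AST = 5, ALT = 9").

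**The concern.** The entry rule and the recovery rule use the same enzymes but different reference points. Entry tolerates values well above normal. Clearance from TOX requires a fixed low grade. For a patient who starts above that grade, returning to the entry value is not enough: the enzymes must become better than they were before any study drug.

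The event is foreseeable. The protocol's own background reports grade 3 enzyme rises with nivolumab in HCC. The steroid exception is the clause that would apply, since Section 3.3.3 says of the nivolumab programme that "Hepatic or gastrointestinal events were managed with treatment interruption and administration of corticosteroids".

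Safety is the primary endpoint, and TOX is the summary named for monitoring and for deciding on later trials. With 15 patients planned per arm, one or two patients classified by their pre-existing liver disease would be visible in that count.

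**Working it through.** The documents give no TOX threshold or operating characteristic, so there is no planned figure to reproduce. The check applies the rule as written to example patients.

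**Inputs**

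- Entry ceiling: 5x ULN (Section 4.1, criterion 6).
- Recovery standard: grade 1 or better within 2 weeks (Section 12.2.1).
- Second 2-week standard: grade 3 falling to grade 2 or lower (Section 7.0).
- Assumption, not printed in the documents: CTCAE 4.0 grades for AST/ALT are grade 1 up to 3x ULN, grade 2 above 3x to 5x, and grade 3 above 5x to 20x. The grade 1 ceiling is varied below.

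**Rule applied.** Suppose the event is at least possibly related, falls in the first 6 weeks and is potentially treatable with steroids, and the enzyme returns exactly to its entry value within 2 weeks. The patient is a TOX if the peak is grade 3 or higher and the entry value is above grade 1.

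| Entry (x ULN) | Entry grade | Peak (x ULN) | Fold rise (peak / entry) | Grade on return to entry | Section 12.2.1 | Section 7.0 standard |
|---|---|---|---|---|---|---|
| 1.5 | 1 | 6 | 4.0 | 1 | not TOX | met |
| 3.0 | 1 | 6 | 2.0 | 1 | not TOX | met |
| 3.1 | 2 | 6 | 1.94 | 2 | TOX | met |
| 4.0 | 2 | 6 | 1.5 | 2 | TOX | met |
| 5.0 | 2 | 6 | 1.2 | 2 | TOX | met |

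All five patients recover completely. The two with the larger relative rises clear the rule, and the three with the smaller rises do not. The three that fail Section 12.2.1 all meet the Section 7.0 standard.

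**Sensitivity to the assumed ceiling.** The affected range of entry values runs from the grade 1 ceiling to 5x ULN:

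- ceiling 2.5x: above 2.5x to 5x;
- ceiling 3x: above 3x to 5x;
- ceiling 5x: no one affected.

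The defect disappears only if grade 1 extends all the way to the entry ceiling.

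**Does another section cure it?**

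- Section 10.3.1.5 does not. A pre-existing value that worsens can still be recorded as an adverse event.
- Section 10.3.1.4 counts worsening by more than one grade, but it concerns baseline signs and symptoms and is not tied to TOX.
- Section 11.1 uses return to baseline, but only for follow-up of serious events.

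**After the fix.** If recovery also includes return to a baseline grade above 1, all five patients are non-TOX. Classification is unchanged for anyone entering at 3x ULN or below.

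**The case against.** The strongest reply is that this is a narrow gap in a deliberately conservative definition. Only patients entering above grade 1 are exposed. The event must be judged at least possibly related. Section 10.3.1.5 also says that abnormal laboratory values are adverse events only if they cause symptoms, are clinically significant or need therapy. The plan attaches no stopping boundary to TOX, so one extra TOX triggers no stated rule. Changing the definition now would be a post hoc change in the favourable direction: the trial is open-label, enrolment has stopped, and the protocol already says that the safety endpoint was reached.

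Much of this stands. The investigator's judgement may remove some cases, but no written rule does so, and *possibly related* is a low bar. The post hoc objection is sound and shapes the fix.

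A reader might infer more than the documents support:

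- **That these TOX use up the two failures allowed by the success rule.** Section 12.2.1 defines success by grade 3 or higher events that force a delay of the planned resection. A short-lived enzyme rise need not do that.
- **That a rate can be had by dividing 9 by 42 from Section 3.3.2.** The 42 are the response-evaluable patients, and no safety denominator is given. That report states neither a 6-week window nor attribution for the enzyme rises. Only events that return to baseline without reaching grade 1 are misclassified, and the share of patients entering above grade 1 is not given.
- **That enzyme rises are the leading grade 3 event.** Section 3.3.2 does not list the other grade 3 events.
- **That uneven baselines would create an apparent safety difference between arms.** No between-arm safety test is planned; Fisher's exact test in Section 12.6 is for response rates.
- **That the and/or wording in criterion 6 admits one enzyme above 5x ULN.** This is a strained reading, and editing the criterion would have no effect with enrolment closed.

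**Conclusion.** The concern holds as a defect in how TOX is counted. Followed as written, Section 12.2.1 classes as an extreme toxicity a patient who enters above grade 1, has an at least possibly related, steroid-treatable grade 3 rise in AST/ALT in the first 6 weeks, and is fully back at baseline within 2 weeks.

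The direction is certain: the rule can add to the TOX count and never reduce it. The size is unknown, because the documents do not report baseline enzyme grades. The conclusion rests on one outside assumption, a CTCAE 4.0 grade 1 ceiling of about 3x ULN, and it survives any ceiling below 5x. It concerns the count used for monitoring and for decisions about future trials, and does not bear directly on the success criterion.

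**What to change.** For endpoint counting only, extend the exception in Section 12.2.1 so that a steroid-treatable event is also cleared if, within 2 weeks, it returns *to the grade at Cycle 1 Day 1 if that grade was above 1*. Keep the protocol-defined TOX count and report the baseline-adjusted count beside it, labelled as a later addition. Replacing the first count would be hard to defend, given that the trial is open-label and enrolment has closed.

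The data should already exist: Table 1 schedules a chemistry panel at Cycle 1 Day 1 in both arms. The cost is one sentence and a baseline-grade column in the TOX listing. A few events leave the adjusted count, but they remain in the protocol-defined count and in the worst-grade tables. A clause based on grade is also coarse. Under the assumed cut-offs, a patient going from 4x to 6x and settling at 4.9x ULN is back in grade 2 and would be cleared, so the listing should show the values as well as the grades.

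Requiring a grade 3 value to be at least one grade worse than baseline would not do the job. Under the same cut-offs, anyone at or below 5x ULN at baseline is grade 2 or lower, so every grade 3 value already meets that condition.

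Sections 7.0 and 12.2.1 judge 2-week recovery by different standards. They should be reconciled, or the protocol should say that they serve different purposes. This point takes no view on which clinical standard is right.
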